Severe Acute Respiratory Coronavirus 2 (SARS-CoV-2) is a new coronavirus strain that emerged from Wuhan, China, at the end of 2019. Subsequently, the infection rapidly spread throughout the world and was declared pandemic by the WHO on 11 March 2020. The virus continues to propagate worldwide, infecting more than 6M people and causing more than 390'000 deaths¹. This new disease challenges health systems all over the world and represents an overwhelming cause of hospitalization. The spectrum of COVID-19 ranges from asymptomatic infection through mild respiratory tract symptoms, to moderate and severe pneumonia. The disease can also manifest through other non-respiratory symptoms, however we will not be describing them in this current protocol as our focus is on respiratory symptoms.

[figure not shown]
We can find many guidelines for hospitalized patients, but in an outpatient setting, our research did not find a lot of data or guidelines, especially for SARS-CoV-2 pneumonia. In the context of COVID-19, health institution and governing bodies such as the NIH and CDC tend to categorizes SARS-CoV-2 symptoms to guide treatment and follow-up. Patients are divide into five categories²:

- *Asymptomatic or Presymptomatic Infection*: test positive for SARS-CoV-2 but have no symptoms
- *Mild Illness*: any of various signs and symptoms (e.g., fever, cough, sore throat, malaise, headache, muscle pain) without shortness of breath, dyspnoea, or abnormal imaging
- *Moderate Illness*: evidence of lower respiratory disease by clinical assessment or imaging and a saturation of oxygen (SaO₂) >93% on room air at sea level.
- *Severe Illness*: respiratory frequency (RF) >30 breaths per minute, SaO₂ ≤93% on room air at sea level, ratio of arterial partial pressure of oxygen to fraction of inspired oxygen (PaO₂/FiO₂) <300, or lung infiltrates >50% seen on thoracic imaging
- *Critical Illness*: respiratory failure, septic shock, and/or multiple organ dysfunction

For patients with moderate or more severe illness, the NIH and CDC recommend admission to a health care facility for close observation². This model was not adopted worldwide, as national and/or medical centers developed their own strategies. To our knowledge, there are no studies involving SARS-CoV-2 outpatients with moderate pneumonia.

As for other bacterial and viral pneumonia, several scores defining an outpatient setting are successfully used; we choose to adapt the CURB-65³ score in the context of SARS-CoV-2 pneumonia. The algorithm included a medical evaluation and paraclinical tests at baseline to ensure the absence of hospitalization criteria⁴ (pneumonia with CURB-65 ≥ 2 or new O₂ dependency or increased O₂ requirements or sustained respiratory rate ≥20 min or decompensated comorbidity or major alteration of the general state). We also took into account the social situation of patients in order to ensure effective isolation measures and support at home. If the management chosen was to keep the patient in an outpatient setting, a follow-up was organised (figure 1): follow-up could be done by phone or by the patient's primary care physician or by an outpatient general medicine consultation at the HUG. For on-site visits, a specific track was established to avoid contact with other patients or healthcare workers

The purpose of this study is to evaluate our strategy for outpatients SARS-CoV-2 moderate pneumonia management in terms of efficacy and patient safety. Our ultimate goal is to validate our first wave management strategy in order to support our future approach in the event of a second wave, and spare the hospital resources by safely keeping at home as many patients as possible.

Version du 02.04.2020 – Groupe Guidelines Covid-1

Figure 1: Moderate pneumonia outpatient management algorithm⁵

2. Objective

Validation of our strategy in terms of safety and efficacy for the treatment of moderate SARS-CoV-2 pneumonia

3. Origin of data and material

We focused on patients consulting in the emergency department at the HUG who remained in an outpatient setting, with pneumonia and moderate illness, defined by individuals who have evidence of lower respiratory disease by clinical assessment or imaging and a saturation of oxygen (SaO₂) $>$ 93% on room air and no other hospitalization criteria (CURB 65 score below 2points).

For patients' follow-up, we have created an aftercare ambulatory unit, open 5/7 days. We were able to conduct 64 consultations between April 2 and May 5, 2020. Every patients had suspected or confirmed SARS-CoV-2 pulmonary tract infection.

The follow-up data was entered into DPI (patient's medical record at HUG) on a specific consultation form. Patients followed in our consultation were contacted between 30 and 60 days after diagnosis by the Covicare team. The Covicare team is call-center composed of medical students and primary care physicians who remotely followed patients with COVID-19 by calling them by phone or telemedicine every day or every other day depending on patients' needs and health status. We will export data from RedCap concerning post-hospitalization, satisfaction survey on our care and oral consent for use of data (ARGOS study CCER number 2020-01273). We will coordinate with the unified HUG database, which is in process by [name].

4. Inclusion Criterias

All persons with suspected or confirmed SARS-CoV-2 pneumonia who consulted in the emergency department of the HUG without criteria for hospitalization⁴ (Pneumonia with CURB-65 ≥ 2 or new O₂ dependency or increased O₂ requirements or sustained respiratory rate ≥ 20 min or decompensated comorbidity or major alteration of the general state) and who have been scheduled for outpatient follow-up in HUG.

5. Exclusion Criterias

Patients with hospitalization criteria⁴

Refusal to consent documentation found in the computerized patient record or oral refusal consent during follow up call.

6. Information and consent of participants

All data are from our daily clinical activity with patients with SARS-CoV-2 pneumonia who visited the Ambulatory Care Unit between April 2, 2020 and May 5, 2020. The Covicare team obtained their consent by telephone for the use of the data at the time of diagnosis. A form was sent to them by message to validate their consent in writing (see attached file name "Consentement à l'utilisation des données en lien avec le COVID19 à des fins de recherche".) Moreover, since the beginning of the outbreak, the HUG screening and emergency sites contain an informative poster mentioning that patient clinical data can be used and collected in clinical studies on COVID-19. Any patient who refuses to allow their data to be used must inform the health care provider at the time of care, and this refusal is insert into DPI. Such patients will be excluded from the study.

7. Scientific methodology

We want to elaborate a retrospective and prospective cohort study.

The statistical analyses will be descriptive only. Given the small sample size of patients, no statistical measures of association will be performed. The data collection period is from April 2 to May 5, 2020. The satisfaction study will be prospective, within the 3 months after diagnosis.

The primary outcome will be secondary hospitalization(s) or death COVID-19 related, until 30 to 60 days from diagnosis

Secondary outcomes will be

- number of unexpected COVID-19 related outpatient visits until day 30 to 60 from diagnosis,
- severity of COVID-19 disease on a 7-points ordinal scale at 30 to 60 days after diagnosis of SARS-CoV-2 (1: not hospitalized, no limitation of activities; 2: not hospitalized, limitation of activities; 3: hospitalized, not requiring supplementary oxygen; 4: hospitalized, requiring supplementary oxygen; 5: hospitalized, on non-invasive mechanical ventilation; 6: hospitalized, on invasive mechanical ventilation or ECMO; 7: death),
- patient satisfaction with management strategies
- estimation of saved costs compared with a strategy of hospitalization of all COVID-19 related pneumonia cases.

8. Obligation to announce

A change in the study's orientation or of the elements mentioned in the decision must be announced beforehand to the competent ethics committee.

9. Data protection: coding and preservation

Removing direct and indirect identifiers will coded data extracted from the DPI. Record ID will be created using a number (1 to 100 for example). This record ID will be reported on the paper survey filled by physicians. Anonymized data will be stored in Microsoft Excel format, protected with a password and on a HUG server, on the responsibility of [name] [name].

10. Procedure concerning non coded data

Data from the physician survey will be coded by [name] [name] and matched with coded data using the record ID. Coded data will be stored in Excel format, protected with a password and on a HUG server, on the responsibility of [name] [name].

11. Data storage

Anonymized coded data will be stored in Excel format, protected with a password and on a HUG server, on the responsibility of [name] [name].

Only [name] [name] can modify the protected Excel file. At each modification, a PDF extract will be made, and named after the date and the initials of the contributor. Paper surveys will be stored in a locked drawer in [name] [name] HUG office.

12. Storage time

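### The objective covers home management by any follow-up route, but the cohort holds only patients followed in HUG, so its event rate cannot stand for the whole strategy

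*Protocol*

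**What the plan says.** The background section, just before Section 2, describes triage with adapted CURB-65 and other hospitalization criteria. For patients who stayed at home it says that "follow-up could be done by phone or by the patient's primary care physician or by an outpatient general medicine consultation at the HUG". It adds that "Our ultimate goal is to validate our first wave management strategy", with a view to a possible second wave.

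Section 2 gives the objective as "Validation of our strategy in terms of safety and efficacy for the treatment of moderate SARS-CoV-2 pneumonia". It names no follow-up route.

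Section 3 describes the population broadly: "We focused on patients consulting in the emergency department at the HUG who remained in an outpatient setting". It then introduces the ambulatory unit and its 64 consultations, without giving the number of patients. On outcome ascertainment it says: "Patients followed in our consultation were contacted between 30 and 60 days after diagnosis by the Covicare team".

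Section 4 limits inclusion to those without hospitalization criteria "and who have been scheduled for outpatient follow-up in HUG". Section 6 says that all data come from "patients with SARS-CoV-2 pneumonia who visited the Ambulatory Care Unit between April 2, 2020 and May 5, 2020".

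Section 7 makes secondary hospitalization or COVID-19-related death, up to 30 to 60 days from diagnosis, the primary outcome. The analysis is descriptive.

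**The concern.** The strategy is a decision to send a patient home, followed by one of several forms of follow-up. Its safety is a property of everyone sent home under that decision. The cohort is the part of that group who were scheduled in HUG and, under Section 6, attended the unit.

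A descriptive proportion still needs a denominator that matches the question. Here a readmission or death in a patient followed only by a primary care physician cannot enter the numerator, and the patient cannot enter the denominator. No section acknowledges this, limits the conclusion accordingly or plans to count the patients left out. A reader planning for a second wave could take the reported rate as the rate for sending such patients home in general, which the data cannot show.

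**Working it through.** The protocol states no figure for this point, so there is none to reproduce. The check sets the sections side by side.

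| Element | Where | Who is covered |
|---|---|---|
| Strategy | Background | Patients kept at home, followed by phone, primary care physician or HUG consultation |
| Objective | Section 2 | The strategy, no route named |
| Population described | Section 3 | Emergency department patients kept as outpatients, no route named |
| Eligibility | Section 4 | Only those scheduled for follow-up in HUG |
| Data source | Section 6 | Only those who attended the unit, 2 April to 5 May 2020 |
| 30 to 60 day contact | Section 3 | Stated for patients of the HUG consultation |

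**Step 1: primary care route.** These patients are in the strategy but fail the Section 4 criterion. They are out on any reading.

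**Step 2: phone-only route.** Section 4 alone might admit them if a HUG phone call counts as follow-up in HUG. Section 6 takes data only from patients who attended the unit, so under Section 6 they are out.

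**Step 3: what the cohort rate can say about the strategy.** Let p be the proportion with the primary outcome in the cohort, s the share of strategy patients outside it, and q the unobserved proportion with the outcome among those outside. Then:

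strategy rate = (1 − s)·p + s·q

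This equals p only if s = 0 or q = p. The protocol gives neither s nor q, and the available text does not say how the route was assigned.

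**Step 4: illustration with assumed values.** Without information on q, the rate is bounded by q = 0 and q = 1, that is, by (1 − s)·p and (1 − s)·p + s. Taking p = 5% as an assumption:

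- s = 10%: 0.90 × 5% = 4.5%, up to 4.5% + 10% = 14.5%
- s = 25%: 0.75 × 5% = 3.75%, up to 3.75% + 25% = 28.75%
- s = 50%: 0.50 × 5% = 2.5%, up to 2.5% + 50% = 52.5%

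These are logical limits, not predictions. In relative terms, with q = r·p, the strategy rate is (1 − s) + s·r times the cohort rate. At s = 0.5, r = 2 gives 0.5 + 1.0 = 1.5 times and r = 0.5 gives 0.5 + 0.25 = 0.75 times. Nothing in the protocol favours one over the other.

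**The case against.** The strongest reply is that the population is disclosed. Section 3 says that the authors created an ambulatory unit for follow-up, and Section 4 names HUG follow-up. The strategy under study could then be HUG triage plus that unit, with the three-route sentence as background only. The routes are also not said to be exclusive, Section 6 is a consent section rather than an eligibility criterion, and the analysis is descriptive with no success threshold.

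Part of this stands. Section 6 is a weaker basis than Section 4 for excluding phone-only patients, and the unit's patients may have had phone calls as well. But the protocol never says that its strategy means only the unit. Section 2 is unrestricted, and patients followed by a primary care physician are outside Section 4 whichever way Section 6 is read.

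Two stronger readings are tempting, and the documents do not support them.

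- A reader might infer that the cohort holds the most closely watched patients, so that its rate flatters the strategy. The protocol does not say so. The unit opened five days in seven with no stated visit frequency, while the Covicare team called COVID-19 patients daily or every other day according to need. If sicker patients were directed to the unit, the cohort rate would overstate the strategy's rate. Figure 1, which might show how the route was assigned, is not in the available text.
- A reader might also infer that the study is set to declare all home management safe. The protocol states an aim to validate, but no decision rule and no pre-written conclusion.

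**Conclusion.** The mismatch is real and lies in the protocol's own text: the objective covers home management by any of three routes, while the eligibility criterion and data source cover HUG follow-up. The cohort can describe outcomes in patients followed at the unit. It cannot, by itself, give the rate of secondary hospitalization or death for the whole strategy.

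Neither direction nor size can be stated. The cohort rate would carry over only if almost all eligible patients took the HUG route or if outcomes did not differ by route, and the protocol supports neither assumption. The cohort itself remains usable. What needs correcting is the scope of the claim, which belongs in the protocol because both the objective and the inclusion criteria are fixed there.

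**What to change.** 1. In the background statement of purpose and in Section 2, restate the objective as the safety and efficacy of outpatient management of moderate SARS-CoV-2 pneumonia with HUG ambulatory-unit follow-up. Limit the conclusion in the same way.
2. Report how many emergency department patients who met the same criteria and were sent home between 2 April and 5 May 2020 took each follow-up route, as far as the DPI records it and data use is permitted. If the route is not recorded, say so.

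This does not extend to outcomes in the other routes. The protocol describes no source of readmission or death data for patients not seen in the unit, and no consent process specific to them.

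The cost is a rewording and, where the record allows, one count. The downside is a narrower claim. Section 8 requires a change of orientation to be announced to the ethics committee in advance, so prior notice may be needed.

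### Section 2 sets out to validate the outpatient strategy, but Section 7 plans only a description of one uncontrolled cohort, with no acceptable event rate stated and efficacy undefined

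*Protocol*

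**What the plan says.** The aim appears three times in the protocol, with two different verbs.

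- Section 1, purpose: "The purpose of this study is to evaluate our strategy for outpatients SARS-CoV-2 moderate pneumonia management in terms of efficacy and patient safety".
- Section 1, goal: "Our ultimate goal is to validate our first wave management strategy in order to support our future approach in the event of a second wave". The same sentence adds the wish to save beds by managing patients at home wherever that is safe.
- Section 2, the whole objective: "Validation of our strategy in terms of safety and efficacy for the treatment of moderate SARS-CoV-2 pneumonia".

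Section 7 fixes the analysis: "The statistical analyses will be descriptive only. Given the small sample size of patients, no statistical measures of association will be performed". It names COVID-19 related secondary hospitalisation or death as the primary outcome, with no benchmark, margin or acceptable rate. Sections 4 and 5 define one group: patients without hospitalisation criteria who were booked for outpatient follow-up. Those who met the criteria are excluded. The only comparison planned is a secondary one, of costs against a policy of admitting every case.

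The one figure on size is in Section 3: "We were able to conduct 64 consultations between April 2 and May 5, 2020". The number of distinct patients is not given.

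**The concern.** To validate is to reach a yes-or-no conclusion, and Section 1 ties that conclusion to practice in a second wave. A descriptive analysis gives an estimate. To get from the estimate to the conclusion, a reader must know what event rate would be tolerable, and the protocol does not say. A very high number of admissions or deaths would plainly count against the strategy. In the plausible middle range, though, the same result could be read as success or failure, depending on a line drawn after the data are seen.

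That risk is real here. The cohort is partly retrospective, and Section 3 describes the follow-up calls in the past tense, so some outcomes may already be known.

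Efficacy raises a second difficulty. The goal sentence suggests that it means the share of patients kept out of hospital, but no definition is given. Undefined, it can be taken as a benefit compared with admission, which a cohort of outpatients alone cannot show.

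**Working it through.** **No figure to reproduce.** The protocol gives no sample size calculation, expected rate, margin or acceptable rate. The check is therefore a comparison of sections, followed by an illustration of how much the unstated line matters.

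**Sections side by side**

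| Needed to declare the strategy validated | What the protocol provides |
|---|---|
| Safety: a rate that the event risk must stay below | Primary outcome named in Section 7; no rate given |
| Efficacy: a definition | None |
| Efficacy relative to admission: a comparator | None; admission of all cases is used for costs only |
| A planned inference | Description only (Section 7) |

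**Illustration: inputs**

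- n = 64 patients. This is an assumption, and a best case: Section 3 counts 64 consultations, and repeat visits would mean fewer patients.
- Lines of 5%, 10%, 15% and 20% for the upper limit. These are assumptions chosen to show sensitivity; none is proposed.

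**Formula.** Exact (Clopper-Pearson) limits for x events in n patients, with B(q; a, b) the q-quantile of the beta distribution:

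- two-sided 95%: lower = B(0.025; x, n − x + 1), upper = B(0.975; x + 1, n − x)
- one-sided 95%: upper = B(0.95; x + 1, n − x)

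For x = 0 the upper limits reduce to 1 − 0.025^(1/64) = 5.6% (two-sided) and 1 − 0.05^(1/64) = 4.6% (one-sided).

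| Events of 64 | Proportion | Two-sided 95% interval | One-sided 95% upper limit |
|---|---|---|---|
| 0 | 0% | 0 to 5.6% | 4.6% |
| 1 | 1.6% | 0.04 to 8.4% | 7.2% |
| 2 | 3.1% | 0.4 to 10.8% | 9.5% |
| 3 | 4.7% | 1.0 to 13.1% | 11.7% |
| 4 | 6.3% | 1.7 to 15.2% | 13.7% |
| 5 | 7.8% | 2.6 to 17.3% | 15.7% |
| 6 | 9.4% | 3.5 to 19.3% | 17.7% |
| 7 | 10.9% | 4.5 to 21.3% | 19.6% |
| 8 | 12.5% | 5.6 to 23.2% | 21.4% |

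**Most events for which the upper limit stays below the assumed line**

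| Assumed line | Two-sided | One-sided |
|---|---|---|
| 5% | none, not even 0 events | 0 |
| 10% | 1 | 2 |
| 15% | 3 | 4 |
| 20% | 6 | 7 |

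Three events of 64 would pass at 15% and fail at 10% under either interval. Two events would pass at 10% one-sided and fail two-sided. So both the line and the type of interval have to be fixed before a result can be called a validation.

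Fewer patients make this harder. With n = 40 (also assumed), 0 events leave a two-sided upper limit of 1 − 0.025^(1/40) = 8.8%.

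**The case against.** The strongest reply is that this is a matter of wording. The purpose sentence in Section 1 says evaluate, the protocol states no hypothesis and claims neither superiority nor non-inferiority, and Section 7 openly limits the analysis to description and says why. Design, outcomes and analysis agree with one another; only the label goes too far. In a local service evaluation, validate may be meant loosely. Much of this stands, and it is why the remedy is mainly rewording. It does not remove the point, because the stronger verb is the formal objective and the one linked to second-wave practice.

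Two stronger readings are tempting and should be resisted.

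- *That a design of this kind can never validate anything.* The documents do not support this. A single-arm cohort could support a safety conclusion if a justified acceptable rate had been set in advance. For safety, what is missing is the criterion.
- *That the study claims home care to be as safe as admission, against the advice it cites.* Section 1 does report that "For patients with moderate or more severe illness, the NIH and CDC recommend admission to a health care facility for close observation", but it goes on to say that this model was not taken up everywhere and that centres set their own policies. No comparative claim is made. The lack of a clinical comparator is also understandable, since the authors write "To our knowledge, there are no studies involving SARS-CoV-2 outpatients with moderate pneumonia". It limits what may be said about efficacy relative to admission, and nothing more.

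It is also fair to say that an interval may be specified in a statistical analysis plan that is not shown. Its absence from the protocol is not counted as a defect here. The mismatch lies between two statements that the protocol itself makes.

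**Conclusion.** The point holds. Sections 1 and 2 promise a validation, while Section 7 provides an estimate with no rule for turning it into one and no definition of efficacy. The data, the outcomes and the planned description are unaffected. What is affected is the headline conclusion, so the change should be made, but it does not call the design into question.

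The size can only be illustrated. With at most 64 patients, even an event-free cohort leaves risks up to about 5% open, and a handful of events can be read either way for lines between 10% and 20%. These figures rest on an assumed number of patients, assumed lines and exact 95% limits. The mismatch between objective and analysis rests on none of them.

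A reader might also want the primary outcome tied to a single day, because the follow-up window runs from 30 to 60 days. That is a separate question and is not needed here.

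**What to change.** 1. Reword Section 2 so that the objective is to describe the outcomes of outpatients with suspected or confirmed moderate SARS-CoV-2 pneumonia, primarily the risk of COVID-19 related secondary hospitalisation or death. Bring the goal sentence in Section 1 into line with the purpose sentence by speaking of evaluating the strategy.
2. Drop efficacy, or define it as the proportion with neither a COVID-19 related secondary hospitalisation nor a COVID-19 related death, and state that it is not a comparative effect. This is the true complement of the primary outcome. Defining it as alive and not readmitted would not be, because a death from another cause would fall in neither group.
3. Report the number of distinct patients and the primary event proportion with an exact 95% interval, and base any statement on safety on its upper limit. An interval for one proportion is not a measure of association, so it fits the descriptive plan. It may be placed in the statistical analysis plan.
4. If the validation wording is kept, the sponsor should state and justify a highest acceptable rate, say whether the interval is one- or two-sided, and disclose whether outcomes were already known when the rate was set.

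**Cost.** Items 1 to 3 need a few reworded sentences and one line of analysis. The downside is a more modest claim and possibly a notice to the ethics committee under Section 8. Item 4 is harder: the authors know of no earlier studies on which to base a rate, and a rate chosen once outcomes are known protects little.

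### Restricting the cohort to patients without hospitalization criteria can drop the strategy's own triage failures from its safety evaluation

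*Protocol*

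**What the plan says.** The introductory section states the purpose: to "evaluate our strategy for outpatients SARS-CoV-2 moderate pneumonia management in terms of efficacy and patient safety". Section 2 repeats it as "Validation of our strategy in terms of safety and efficacy for the treatment of moderate SARS-CoV-2 pneumonia". The introductory section also describes the strategy's first step: "The algorithm included a medical evaluation and paraclinical tests at baseline to ensure the absence of hospitalization criteria".

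Three sections then define who is studied:

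- Section 3 takes "patients consulting in the emergency department at the HUG who remained in an outpatient setting" and further requires that no other hospitalization criterion be present.
- Section 4 includes persons "who consulted in the emergency department of the HUG without criteria for hospitalization" who were also scheduled for follow-up at the hospital.
- Section 5 excludes "Patients with hospitalization criteria", citing the same hospital guideline as Section 4 but naming no time point.

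Section 7 calls the study a retrospective and prospective cohort, plans descriptive analysis only, and gives the endpoint: "The primary outcome will be secondary hospitalization(s) or death COVID-19 related, until 30 to 60 days from diagnosis". The protocol plans no count or separate report of outpatients who turn out to have met a criterion when they were sent home.

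**The concern.** The decision to send a patient home is part of what is being evaluated. A patient discharged with a criterion present (an overlooked oxygen need, say, or a CURB-65 score added up too low) was managed by the strategy and is a failure of its first step. If eligibility is settled from the records, that patient leaves the cohort, and the reported rate becomes conditional on triage having been right. The stated aim is to support the approach in a second wave, where error-free triage cannot be assumed.

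Timing adds to this. The collection window (2 April to 5 May 2020) is closed, and Section 3 describes the follow-up calls at 30 to 60 days in the past tense. Some criteria call for judgement, such as a decompensated comorbidity or a marked decline in general condition. Someone applying them to a record that already shows an admission may find a criterion more readily. The estimate of saved costs would be affected in the same direction, because dropping a patient who was later admitted also drops the cost of that admission.

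**Working it through.** The protocol states no event rate, sample-size calculation or power figure, so there is no figure of its own to reproduce. The check is a reading of the text, followed by an illustration.

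**Text.**

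1. The criteria check belongs to the strategy (introductory section).
2. The strategy is the object of validation (introductory section, Section 2).
3. Absence of the criteria is a condition of entry in Section 3, again in Section 4, and again in Section 5.
4. Taken together, a patient managed by the strategy despite a criterion is outside the cohort as written. Deleting the Section 5 line alone would not bring that patient back.

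**Illustration with assumed counts.** Take N = 64 patients. The protocol's 64 is a number of consultations, so using it as a patient count is an assumption. Suppose 4 were sent home with a criterion present and 2 of them had an event, while 4 of the other 60 had an event.

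- All patients sent home: (4 + 2)/64 = 6/64 = 9.4% (exact 95% CI 3.5% to 19.3%).
- After the restriction: 4/60 = 6.7%.
- Difference: 2.7 percentage points.

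**Range.** Let k be the number sent home with a criterion, q their event rate, and p the rate in the remaining N − k. Then

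full-cohort rate = [(N − k)p + kq]/N, and the understatement = full-cohort rate − p = k(q − p)/N.

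For example, p = 10%, k = 3 and q = 50% give (61 × 0.10 + 3 × 0.50)/64 = 7.6/64 = 11.9%, against 10.0% when the three are left out. Understatement in percentage points, with N = 64:

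| p | k | q = 20% | q = 50% |
|---|---|---|---|
| 5% | 1 | 0.23 | 0.70 |
| 5% | 3 | 0.70 | 2.11 |
| 5% | 6 | 1.41 | 4.22 |
| 10% | 1 | 0.16 | 0.63 |
| 10% | 3 | 0.47 | 1.88 |
| 10% | 6 | 0.94 | 3.75 |
| 15% | 1 | 0.08 | 0.55 |
| 15% | 3 | 0.23 | 1.64 |
| 15% | 6 | 0.47 | 3.28 |

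The range is about 0.1 to 4.2 points. The formula gives zero when k = 0 or q = p.

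**The case against.** **The target may be patients who meet the outpatient rule.** Restricting the cohort to patients in whom the algorithm calls for outpatient care answers a legitimate question, and for that target the exclusion is not a bias. This stands: the protocol does not say which target it means. But its aim of validating the strategy used in the first wave points at least as much to the strategy as delivered, and reporting both populations serves either target.

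**No re-adjudication is described.** The protocol nowhere says that a chart reviewer will override the emergency physician. If the criteria mean those judged present at the visit, a missed one stays in the cohort. This also stands, and it is why the claim is that patients can be removed, not that they will be. The text does not say whose judgement governs.

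**A declined admission is not a triage failure.** Correct: triage worked and the patient refused. Such patients need to be identified separately.

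**The shift is small beside the sampling error.** In the illustration, 2.7 points compares with an interval of 3.5% to 19.3%. True, but imprecision does not cancel a systematic omission, and in a purely descriptive study the point estimate is what readers will carry away.

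**A stronger reading that the documents do not support.** Because Section 5 names no time point, a reader might infer that patients who first meet a criterion during follow-up are also excluded. On that reading 6/64 would become 0/58 and the primary outcome would be emptied. Section 4 ties the criteria to the emergency consultation, the introductory section places the "medical evaluation and paraclinical tests at baseline to ensure the absence of hospitalization criteria", and the primary outcome counts later hospitalization and death as events. This is a gap in wording, not a planned exclusion.

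**Conclusion.** The point holds in a limited form. Sections 3, 4 and 5 jointly restrict the cohort to patients without hospitalization criteria, while the check for those criteria is part of the strategy whose safety is to be validated. Applied from largely completed records, the restriction can remove patients sent home despite a criterion. The event rate can then be too low for the strategy as delivered.

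A reader might go further and state that the rate is biased downward. The protocol does not support that, since it gives neither the number of such patients nor their risk. The conclusion rests on two conditions: that such patients exist, and that their event rate is higher than that of the others. The second is plausible, because the criteria are the centre's own markers for admission, but it is not shown. Under the assumed scenarios the understatement is about 0.1 to 4.2 percentage points, with 9.4% against 6.7% as a worked case. It also depends on taking the strategy as delivered to be the target.

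**What to change.** Align Sections 3, 4 and 5 in these respects:

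- Define the main cohort as every patient with suspected or confirmed SARS-CoV-2 pneumonia whom the emergency department sent home and scheduled for follow-up at the hospital.
- Remove the presence of hospitalization criteria as an exclusion applied from the records.
- Flag patients who met a criterion at the index emergency visit as algorithm deviations, and identify declined admissions separately among them.
- Report the primary outcome for all patients, and again without the deviations.

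As a wording clarification only, state that the criteria refer to the index emergency visit and that later deterioration is an outcome, not a ground for exclusion.

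The cost is small text edits in three sections and one extra line in the descriptive table. The headline rate may look slightly less favourable. In return, both possible targets are shown, and a patient can no longer be dropped by someone who already knows the outcome.
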